6.1.2.2 Dose Limiting Toxicity

N/A

6.1.2.3 Dose Modifications

Fostamatinib dose modification is recommended based on individual safety and tolerability. Management of some adverse reactions may require dose-interruption, reduction, or discontinuation.

A dose reduction schedule (DRS) is provided below. For example, if a patient is on the maximum (300mg total daily dose) at the time of an adverse reaction, the first dose reduction would be from 300mg/day to 200mg/day.

Dose Reduction Schedule (DRS)		
Total daily dose	Dosing Schedule	
	Morning	Evening
300mg	150mg	150mg
200mg	100mg	100mg
150mg	150mg ¹	---
100mg ²	100mg ¹	---

¹: Once daily fostamatinib should be taken in the morning.

²: If further dose reduction below 100mg/day is required, stop fostamatinib

Treatment may be delayed for a maximum of 14 days after holding the treatment for toxicities that develop and do not resolve as defined at 6.1.2.3 (neutropenia, LFT elevation, and diarrhea). The timing of subsequent lab and the study week are then adjusted to the study week that was stopped.

The recommended dose modification for adverse reactions are as the following:

	Recommended action
Hypertension Stage 1: systolic between 130-139 or diastolic between 80-89 mmHg	
 Initiate or increase dosage of antihypertensive medication for patients with increased cardiovascular risk, and adjust as needed until BP is controlled. If the BP target is not met after 8 weeks, reduce fostamatinib to next lower daily dose (refer to DRS). Consider cardiology consult

Stage 2: systolic at least 140 or diastolic at least 90 mmHg	
 Initiate or increase dosage of antihypertensive medication, and adjust as needed until BP is controlled. If BP remains 140/90 mmHg or higher for more than 8 weeks, reduce fostamatinib to next lower daily dose (refer to DRS). If BP remains 160/100 mmHg or higher for more than 4 weeks despite aggressive antihypertensive therapy, interrupt or discontinue fostamatinib. Consider cardiology consult
Hypertensive crisis: systolic over 180 and or diastolic over 120 mmHg	
 Interrupt or discontinue fostamatinib. Initiate or increase dosage of antihypertensive medication, and adjust as needed until BP is controlled. If BP returns to less than the target BP, resume fostamatinib at same daily dose. If repeat BP is 160/100 mmHg or higher for more than 4 weeks despite aggressive antihypertensive treatment, discontinue fostamatinib. Consider cardiology consult
Hepatotoxicity	
AST/ALT abnormal at enrollment but < 3x ULN	Recheck LFTs every week to ensure it is still <3x ULN. Patient may have it checked locally and have results faxed to the NIH.
Increase in AST/ALT by x3 from level at the time of enrollment but less than 3 x ULN	
If patient is symptomatic (e.g., nausea, vomiting, abdominal pain):
 
 Interrupt fostamatinib. Recheck LFTs every 72 hours until ALT/AST values are no longer elevated (below 1.5 x ULN) and direct bilirubin (DBL) remains less than 2 x ULN. Resume fostamatinib at next lower daily dose (refer to DSR). 
If patient is asymptomatic:
 
 Recheck LFTs every 72 hours until ALT/AST are below 1.5 x ULN) and DBL remains less than 2 x ULN. Consider interruption or dose reduction of fostamatinib if ALT/AST and DBL remain in this category (AST/ALT is less than 3x ULN; and DBL remains less than 2 x ULN). If interrupted, resume fostamatinib at next lower daily dose (refer to DSR) when ALT/AST are no longer elevated (below 1.5 x ULN) and total BL remains less than 2 x ULN.

Abbreviated Title: Fostamatinib for post-transplant cytopenias

Version Date: 11/28/2023

Increase in AST/ALT by x3 ULN and DBL is less than 2 x ULN	
Interrupt fostamatinib. Recheck LFTs every 72 hours:
 
 • If AST and ALT decrease, recheck until ALT and AST are no longer elevated (below 3 x ULN) and total BL remains less than 2 x ULN; resume fostamatinib at next lower daily dose (refer to DSR). Per PI discretion, subject can be re-escalated one level at a time until back to the maximum tolerable dose • If AST/ALT persist at 5 x ULN or higher for 2 weeks or more, discontinue fostamatinib.
AST/ALT is 3 x ULN or higher and DBL is greater than 2 x ULN	Discontinue fostamatinib
Elevated unconjugated (indirect) BL in absence of other LFT abnormalities	Continue fostamatinib with frequent monitoring since isolated increase in unconjugated (indirect) bilirubin may be due to UGT1A1 inhibition or active hemolysis
Diarrhea	
Diarrhea	
 • Manage diarrhea using supportive measures (e.g., dietary changes, hydration and/or antidiarrheal medication) early after the onset until symptom(s) have resolved. • If symptom(s) become severe (Grade 3 or above), temporarily interrupt fostamatinib. • If diarrhea improves to mild (Grade 1), resume fostamatinib at the next lower daily dose (refer to DSR).
Neutropenia	
Neutropenia	
 • If absolute neutrophil count decreases (ANC less than $1.0 \times 10^9/L$) and remains low after 72 hours, or the neutropenia can be attributed to other causes (see below), patient can receive standard dose (5mcg/kg or rounded to the closest vial or syringe size) filgrastim at the discretion of the primary team and continue fostamatinib. If neutropenia responds to filgrastim (ANC greater than $1.5 \times 10^9/L$), patient should continue fostamatinib. • If no other causes are identified and the neutropenia is attributed to fostamatinib, or patient does not respond to, or cannot receive filgrastim, temporarily interrupt fostamatinib until neutropenia resolves (ANC greater than $1.5 \times 10^9/L$), and resume fostamatinib at the next lower daily dose (refer to DSR).
Febrile neutropenia	Febrile neutropenia is a life-threatening complication and urgent broad-spectrum

	
antibiotics, as well as an aggressive search for the source and microbial cause of the episode.
 
 • First febrile neutropenia: hold fostamatinib then restart at the next lower dose level after resolution of febrile neutropenia (refer to DSR) • Second febrile neutropenia on the next lower dose level: stop fostamatinib and remove the patient from study
--	--

- In the event that the subject is unable to tolerate 100 mg BID, the dose can be reduced to 150mg daily with re-assessment. If intolerable AEs with 150 mg daily, dose can be reduced to 100 mg daily. If unable to tolerate 100mg daily, patient will stop fostamatinib and will be off study. Intolerance is considered as any grade 3-4 AEs, probably or definitely related to fostamatinib, or any grade AE which, at the PI's discretion, appears to be distressing enough to the patient to lead to the drug's discontinuation. If the adverse events resolved and subject tolerates the dose reduction with no recurrence of AE, per PI discretion subject can be re-escalated one level at a time until back to the maximum tolerable dose.
- Causes of neutropenia in a AHCT recipient may include: infections such as cytomegalovirus infection, medication such as ganciclovir or other antibiotics, immunosuppressants such as mycophenolate or ruxolitinib, graft failure, relapse of primary disease. If neutropenia occurs, we will perform an extensively work up on the patient for the other causes stated above, and/or hold other potential culprit medications. We will give filgrastim to patients while doing the above work up. If no other causes are found, and the neutropenia does not recover, or recurs, with holding other medications, we will conclude that fostamatinib is contributing to the development of neutropenia.
- GvHD may mimic adverse events. If holding fostamatinib according to the DSR does not reverse the diarrhea, abdominal pain, transaminase elevation, AND there are no other causes (such as infection) identified, we will consider the cause of the adverse events to possibly be related to GVHD. In such circumstances, we will make every effort possible to perform biopsies of the involved organ systems to confirm the diagnosis of GvHD.

Dose adjustment for platelet counts and hemoglobin are as the following:

Thrombocytosis	
PLT $\geq 200 \times 10^9 /L$ to $\leq 400 \times 10^9 /L$ at any time	
 • Decrease the dose to the next lower dose level. Wait 2 weeks to assess the effects of this and any subsequent dose adjustments.
PLT $> 400 \times 10^9 /L$ at any time	
 • Stop fostamatinib. Increase the frequency of platelet monitoring to twice weekly. • Once the platelet count is $< 150 \times 10^9 /L$, resume fostamatinib at the next lower dose level
PLT $> 400 \times 10^9 /L$ after 2 weeks of therapy at the lowest dose of fostamatinib	
 • Discontinue fostamatinib
Polycythemia	
Hb $\geq 13 \text{ g/dL}$ to $\leq 15 \text{ g/dL}$ at any time	
 • Decrease the dose to the next lower dose level. Wait 2 weeks to assess the effects of this and any subsequent dose adjustments.

Abbreviated Title: Fostamatinib for post-transplant cytopenias

Version Date: 11/28/2023

Hb > 15 g/dL at any time	
 Stop fostamatinib. Increase the frequency of platelet monitoring to twice weekly. Once the Hb <13 g/dL, resume fostamatinib at the next lower dose level
Hb > 15 g/dL after 2 weeks of therapy at the lowest dose of fostamatinib	
 Discontinue fostamatinib

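### Two restart rules in the hepatotoxicity table test total bilirubin where every other rule tests direct, so a subject with hemolysis can fail to restart because of the disease under treatment

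*Combined protocol and SAP*

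**What the plan says.** Section 6.1.2.3 governs holding, restarting and stopping fostamatinib for raised liver tests.

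- **AST/ALT tripled from enrollment but below 3 x ULN, symptomatic.** Hold, and recheck until ALT/AST are below 1.5 x ULN and "direct bilirubin (DBL) remains less than 2 x ULN"; then resume one dose level down.
- **Same row, asymptomatic.** "Recheck LFTs every 72 hours until ALT/AST are below 1.5 x ULN) and DBL remains less than 2 x ULN". Then: "Consider interruption or dose reduction of fostamatinib if ALT/AST and DBL remain in this category". If the drug was interrupted, resume "when ALT/AST are no longer elevated (below 1.5 x ULN) and total BL remains less than 2 x ULN".
- **3 x ULN row.** Entry: "Increase in AST/ALT by x3 ULN and DBL is less than 2 x ULN". The drug is interrupted and liver tests are repeated every 72 hours. If AST and ALT fall, "recheck until ALT and AST are no longer elevated (below 3 x ULN) and total BL remains less than 2 x ULN"; then resume one level down.
- **Permanent stops.** One is "AST/ALT is 3 x ULN or higher and DBL is greater than 2 x ULN". The other has no bilirubin term: "If AST/ALT persist at 5 x ULN or higher for 2 weeks or more, discontinue fostamatinib".

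The next row of the table covers a raised indirect bilirubin with no other liver test abnormality. The drug is continued, because such a rise may come from UGT1A1 inhibition or from active hemolysis.

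Section 5.2 excludes on direct bilirubin at 2 x ULN or more and sets no limit on total. Sections 2.2 and 5.1 admit autoimmune and alloantibody-mediated hemolytic anemia, and 5.1 lists raised indirect bilirubin among the supporting laboratory findings.

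**The concern.** Total bilirubin includes the indirect fraction, which hemolysis raises. Entry to the trial, entry to the hepatotoxicity rows and the bilirubin-based permanent stop all use direct bilirubin, which keeps hemolysis out of the liver rules. The two restart rules bring it back in. Read literally, a subject whose liver injury has resolved stays off drug because of the condition the trial treats.

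Two things are at stake. One is drug exposure in affected subjects. Under 6.1.2.3 a hold of up to 14 days shifts the study weeks, so the loss is time; past 14 days, section 7.1 provides for withdrawal. The other is consistency: in a multicenter study, some sites may apply total bilirubin as printed and others may read it as direct.

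**Working it through.** **Step 1: count the 2 x ULN bilirubin tests in the hepatotoxicity rows.**

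| Test | Fraction |
|---|---|
| Symptomatic recheck and resume | direct |
| Asymptomatic recheck | direct |
| Asymptomatic trigger to consider interruption or reduction | direct |
| Asymptomatic resume | **total** |
| Entry to 3 x ULN row | direct |
| 3 x ULN row, recheck and resume | **total** |
| Bilirubin-based permanent stop | direct |

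That is 5 direct + 2 total = 7. With the exclusion limit in 5.2, the balance is 6 direct against 2 total.

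**Step 2: is the switch deliberate?** Within one row, an interrupted symptomatic subject restarts on direct bilirubin and an interrupted asymptomatic subject on total, both at ALT/AST below 1.5 x ULN. The milder case gets a different test, with no reason given. Both restart rules also say that total bilirubin *remains* below 2 x ULN, yet these rows have set only the direct fraction below that limit. Both points suggest leftover text.

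**Step 3: can the two tests disagree?** Total = direct + indirect, so the total test fails once indirect reaches 2 x ULN(total) − direct. The documents give no reference limits. I assume ULN 1.0 to 1.2 mg/dL for total and 0.2 to 0.4 mg/dL for direct, with the subject's direct bilirubin at its ULN, so the direct test always passes.

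- Lowest threshold: 2 × 1.0 − 0.4 = 1.6 mg/dL indirect.
- Highest threshold: 2 × 1.2 − 0.2 = 2.2 mg/dL indirect.
- Example with limits 1.2 and 0.3: direct 0.3 + indirect 2.5 = 2.8, which is not below 2.4, so restart fails. Direct, at 0.3, is below 2 × 0.3 = 0.6.

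**Step 4: does the indirect-bilirubin row rescue this subject?** Not clearly. It tells the investigator to continue the drug and does not mention resuming after a hold. It also requires that no other liver test be abnormal. The 3 x ULN row allows restart with ALT/AST anywhere below 3 x ULN, a range that the table's first hepatotoxicity row treats as abnormal. The restart rules themselves describe those levels as no longer elevated, so the opposite reading is also open.

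**Step 5: how long could the hold last?** With rechecks every 72 hours, floor(14 × 24 / 72) = floor(4.67) = 4 fall within the limit, on days 3, 6, 9 and 12; the next is day 15. On that schedule each recheck failed on total bilirubin alone adds 3 days. To pass 14 days for this reason alone, total bilirubin must stay at or above 2 x ULN at every recheck from ALT/AST recovery to day 12. That is 4 rechecks if ALT/AST recover by day 3, and 1 if they recover only by day 12.

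**The case against.** The strongest reply is that this is a slip in terminology that any hepatologist would read through. The actions are headed as recommendations, and in the asymptomatic branch interruption is only to be considered. Once ALT/AST reach the restart level, a raised indirect fraction can fairly be called isolated, and the table then says to carry on. That argument is better at 1.5 x ULN than at 3 x ULN, where a mild rise can persist. It limits the harm but leaves the printed rule wrong.

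The route to withdrawal is also conditional at each step. The 14-day limit concerns unresolved toxicity, and it is arguable that none remains once the enzymes have recovered. Sections 9.1 and 9.2.1 score non-response on this route only if the stop is attributed to drug-related toxicity or AE. Nothing forbids a test sooner than 72 hours, so the gap between day 12 and day 15 depends on the assumed schedule. All of this stands, and it is why the point is minor.

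Numbers are small too. Section 2.3.1 gives AST/ALT above 3 x ULN in 9% of treated patients. If that rate carried over, 0.09 × 20 = 1.8 subjects would reach the 3 x ULN level, or 0.09 × 28 = 2.5 with the 8 possible extra subjects. Only those with hemolysis and discordant fractions would be affected. The 9% does not come from this population and does not cover the tripled-from-enrollment row, so it is a rough guide only.

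Last, a stricter test for re-exposure than for stopping can be sensible caution. Here it does not fit: the symptomatic rule uses direct. Nor is the total test uniformly stricter. Under the Step 3 limits, a subject with direct bilirubin at exactly 2 x ULN fails the direct test but passes the total test whenever indirect is below 2 × ULN(total) − 2 × ULN(direct). That bound runs from 2.0 − 0.8 = 1.2 to 2.4 − 0.4 = 2.0 mg/dL.

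**Conclusion.** The concern holds, at minor severity. Two of seven bilirubin tests use the wrong fraction for this population, and both are restart rules. Followed as written, they can keep a subject with hemolysis off drug after ALT/AST have recovered.

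Confidence is high for the mismatch and its literal effect. It does not extend to frequency, which the documents do not allow to be estimated. The mg/dL thresholds rest on assumed reference limits, and the hold length on a strict 72-hour schedule. Sample size, primary analysis and stopping rules are not affected.

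**What to change.** In section 6.1.2.3, replace total BL with DBL in the restart rule for interrupted asymptomatic subjects and in the recheck-and-resume rule of the 3 x ULN row. All seven tests then use the same fraction as the exclusion limit. Add to the indirect-bilirubin row: *An indirect rise alone does not prevent resumption after an LFT hold once ALT/AST meet the resume level.*

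The cost is two word changes and one sentence. Section 8.4.7 already lists both total and direct bilirubin for close follow-up, so no new test is needed. The downside is a slightly less strict restart test for subjects with a mainly indirect rise. Both permanent stops are unchanged. If the sponsor does want total bilirubin for restart, the section should say so, give the reason, and apply it to the symptomatic branch as well.

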5.2 EXCLUSION CRITERIA

- Severe psychiatric illness or mental deficiency sufficient to make making informed consent impossible
- Positive pregnancy test for women of childbearing age within 1 week or being actively lactating
- Immune mediated cytopenia responsive to the standard of care treatment
- Immune mediated cytopenia due to other autoimmune causes, such as systemic lupus erythrocytosis, chronic lymphocytic leukemia
- Patients who have previously received or currently take fostamatinib post-allogeneic transplant
- Non-immune mediated cytopenias. Etiologies including, but not limited to, cytopenias due to HIV infection, lymphoproliferative disorders, myelodysplasia/acute leukemia, drug-induced thrombocytopenia, thrombotic microangiopathies, acute bleeding, consumptive coagulopathy, fever, infections leading to cytopenia, medications induced cytopenias, thrombotic microangiopathies (disseminated intravascular coagulation), splenomegaly or hemophagocytic lymphohistiophagocytosis, relapse of primary disease.
- Patients with neutropenia, defined as absolute neutrophil count $\leq 1.0 \times 10^9/L$, will be excluded
- Uncontrolled hypertension (systolic blood pressure ≥ 140 mmHg or diastolic blood pressure ≥ 90 mmHg)

Abbreviated Title: Fostamatinib for post-transplant cytopenias

Version Date: 11/28/2023

- ALT or AST ≥ 3 times the upper limit of normal, or direct bilirubin ≥ 2 times the upper limit of normal
- Patients who have a history of medical disorders, that in the investigator's opinion, could affect the conduct of the study or the absorption, metabolism or excretion of the study drug are excluded.
- Patients with lymphoma/chronic lymphocytic leukemia, hepatitis, or HIV associated with ITP/wAIHA
- Patients with evidence of graft rejection (based on clinical suspicion supported by BM biopsy data and/or chimerism studies and/or MLR)
- Subjects recently treated (within 30 days) with cytokine-targeting biologics (anti-TNF, IL6) or B-cell or plasma-cell depleting antibody.
- Other cancers except that for which the transplant was done < 2 years before study entry, except non-melanoma skin cancer or carcinoma in situ of the uterine cervix or breast

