8.4.3.2 Relationship to Study Intervention

All grade 3 and 4 AEs, clinically significant laboratory abnormalities, and all SAEs occurring from the time of study drug initiation through the end of the 16th week must have their relationship to study intervention assessed by the investigator who examines and evaluates the participant based on temporal relationship and his/her clinical judgment. The degree of certainty about causality will be graded using the categories below. In a clinical trial, the study product must always be suspect.

- **Definitely Related** – There is clear evidence to suggest a causal relationship, and other possible contributing factors can be ruled out. The clinical event, including an abnormal laboratory test result, occurs in a plausible time relationship to study intervention administration and cannot be explained by concurrent disease or other drugs or chemicals. The response to withdrawal of the study intervention (de-challenge) should be clinically plausible. The event must be pharmacologically or phenomenologically definitive, with use of a satisfactory rechallenge procedure if necessary.
- **Probably Related** – There is evidence to suggest a causal relationship, and the influence of other factors is unlikely. The clinical event, including an abnormal laboratory test result, occurs within a reasonable time after administration of the study intervention, is unlikely to be attributed to concurrent disease or other drugs or chemicals, and follows a clinically reasonable response on withdrawal (rechallenge). Rechallenge information is not required to fulfill this definition.
- **Possibly Related** – There is some evidence to suggest a causal relationship (e.g., the event occurred within a reasonable time after administration of the trial medication). However, other factors may have contributed to the event (e.g., the participant's clinical condition, other concomitant events). Although an AE may rate only as "possibly related" soon after discovery, it can be flagged as requiring more information and later be upgraded to "probably related" or "definitely related", as appropriate.

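### Section 6.1.2.3 gives opposite orders for drug-attributed neutropenia that responds to filgrastim, and filgrastim itself confounds the test used for attribution

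*Combined protocol and SAP*

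**What the plan says.** The neutropenia row of the dose-modification table in 6.1.2.3 has two bullets.

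- **Bullet 1** covers an ANC that falls below 1.0 × 10⁹/L and "remains low after 72 hours, or the neutropenia can be attributed to other causes (see below), patient can receive standard dose" "filgrastim at the discretion of the primary team and continue fostamatinib" (the dose in brackets is left out here). Its last sentence deals with responders, meaning ANC above 1.5: "patient should continue fostamatinib". That sentence sets no condition on cause.
- **Bullet 2** reads "If no other causes are identified and the neutropenia is attributed to fostamatinib, or patient does not respond to, or cannot receive filgrastim, temporarily interrupt" the drug until ANC is above 1.5, then restart at the next lower daily dose.

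The notes after the table list other possible causes, plan a work-up and/or the holding of other suspect medicines, and continue: "We will give filgrastim to patients while doing the above work up. If no other causes are found, and the neutropenia does not recover", or comes back, while those medicines are held, fostamatinib is taken to be contributing.

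Separately, 8.4.3.2 has the investigator grade relatedness for grade 3 and 4 events, clinically significant laboratory abnormalities and all SAEs, with the reminder "In a clinical trial, the study product must always be suspect". Section 9.3.4 B monitors treatment-related SAEs.

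**The concern.** Two problems sit in the same few lines.

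First, the bullets are not mutually exclusive. Bullet 1 opens on persistence or on another cause, so it is not confined to neutropenia explained by something else, and its responder sentence is unconditional. Bullet 2 turns on attribution. A subject can satisfy both.

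Second, attribution in the notes depends on whether the ANC recovers, yet it is observed while a drug is given to raise the ANC. The table leaves filgrastim to the primary team; the notes say it is given.

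What is at stake is exposure and counting. Up to four sites (the NIH Clinical Center plus up to three others) could handle the same subject differently. One order keeps the current dose. The other lowers it and starts a hold that, under 7.1, leads to withdrawal if it exceeds 14 days. If a serious event is graded unrelated because filgrastim corrected it, it is missing from the count in 9.3.4 B.

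**Working it through.** **1. Listing the cases.** Take a subject with ANC below 1.0, still low at 72 hours. Three yes/no facts matter: another cause found, attribution to fostamatinib, response to filgrastim. Subjects who cannot receive filgrastim go with non-responders, as in bullet 2. That gives 2 × 2 × 2 = 8 combinations. The two with both another cause and attribution are set aside, because bullet 2 and the notes require that no other cause be found. Six remain. "Continue" is read from the responder sentence of bullet 1. "Interrupt" is read from bullet 2: (no other cause and attributed) or no response.

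| Other cause | Attributed | Responds | Bullet 1 | Bullet 2 |
|---|---|---|---|---|
| no | no | no | – | interrupt |
| yes | no | no | – | interrupt |
| no | no | yes | continue | – |
| yes | no | yes | continue | – |
| no | yes | no | – | interrupt |
| no | yes | yes | **continue** | **interrupt** |

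One row conflicts.

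**2. Whether that row can occur.** Under the notes, neutropenia that recurs with no other cause found is attributed to fostamatinib. If the recurrence also responds to filgrastim, the subject is in the last row. An investigator who judges a first episode related on timing alone puts a responder there too.

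**3. The attribution test.** During the work-up fostamatinib continues, other suspect medicines may be held, and filgrastim is given. The plan itself treats filgrastim as able to bring the ANC above 1.5.

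- Drug-caused neutropenia that filgrastim corrects: ANC recovers.
- Neutropenia from another source that filgrastim corrects: ANC recovers.

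The observation is the same, so recovery on filgrastim cannot separate the two. A single drug-caused episode, corrected and not recurring, does not meet the criterion in the notes.

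**4. The separate relatedness grading.** In 8.4.3.2 the probable and definite categories refer to the response when the drug is withdrawn. That is not observed if fostamatinib continues. The possible category needs only some evidence, such as timing, so it stays open. Section 9.3.4 B does not say which categories make an SAE treatment-related.

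**5. Scale.** Section 2.3.1 gives neutropenia in 6% of patients; 3.1 plans 20 subjects. Expected cases of any neutropenia: 20 × 0.06 = 1.2. If the rate here is assumed to lie between 3% and 12%, the range is 20 × 0.03 = 0.6 to 20 × 0.12 = 2.4. The conflicting row is a subset, and the documents give no fraction for it.

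**6. The safety boundary.** With the Beta(1, 3) prior and the 90% posterior criterion, the boundaries in 9.3.4 B reproduce at every n from 3 to 20. Exact stopping probabilities are 0.7%, 8.3%, 18.4%, 32.9%, 66.8% and 90.2%, against the stated 1%, 8%, 19%, 33%, 67% and 90%. The rule is sound given its input. The input is what attribution affects: with 8 to 10 subjects the boundary is 5 events, so if one of five true treatment-related SAEs is graded unrelated, the count is 4 and the boundary is not reached. This applies only to serious events.

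**The case against.** The strongest reply is that the bullets are steps in time: bullet 1 applies during the work-up and bullet 2 once it has concluded. On that reading a subject whose ANC goes from 0.8 to 2.0 on filgrastim, with no other cause found, is simply not attributed and gets one order. That is right. A reader might infer that every such responder receives both orders, but the text does not support this: bullet 2 also needs attribution. The sequence is not written down, however, and the unconditional responder sentence still collides with bullet 2 for an attributed recurrence.

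A reader might also infer that the plan clears fostamatinib whenever filgrastim works. It does not say so. The notes state when the drug will be implicated; they do not say it is otherwise exonerated. In 8.4.3.2 the not-related category requires a documented, definitive alternative, so neutropenia with no other cause found cannot be placed there. These are real safeguards, as is the recurrence limb. They are partial: a single corrected episode escapes the recurrence limb, and continued dosing removes the withdrawal evidence on which the stronger categories lean.

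Febrile neutropenia has its own row, which holds the drug without reference to attribution or filgrastim response. That limits the reach of the dosing conflict for the infection-related event.

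**Conclusion.** The point stands in a narrow form. Section 6.1.2.3 contradicts itself in one of six cases, states filgrastim use in two incompatible ways, and rests attribution partly on an observation that filgrastim confounds. Missed attribution is a possibility, not a certainty. The frequency of the conflicting case cannot be derived from the documents. The 1.2 expected cases concern any neutropenia and assume that the 6% carries over to transplant recipients; the documents do not say that it uses the ANC definition in 6.1.2.3.

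Three larger claims are tempting and should not be made.

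- The chance of at least one neutropenia in 20 subjects at 6% is 1 − 0.94²⁰ = 71%. That is not the chance of meeting this conflict.
- Section 5.2 excludes "Patients with neutropenia, defined as absolute neutrophil count" at or below 1.0, while resumption needs more than 1.5. A reader might call this an inconsistency, but entry and resumption after toxicity are different decisions and may have different thresholds.
- A reader might infer that missed attribution shifts subjects between the evaluability categories of 9.1. The subject in question responds to filgrastim and stays on drug, so there is no discontinuation to classify.

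It deserves correction because the wording governs both dosing and the counting of related events in a known risk of the drug.

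**What to change.** Reconcile the two bullets of the neutropenia row with each other and with the notes on causes, so that every combination in the table above leads to one instruction and filgrastim is described the same way in both places. Which clinical rule applies is for the sponsor to decide.

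For adverse-event grading only, add a sentence stating that ANC recovery while filgrastim is being given is not by itself evidence against relatedness under 8.4.3.2, and that serious events graded related are counted in 9.3.4 B. This sentence need not settle the dosing question.

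The cost is a few sentences and no new tests or visits. The small downside is that slightly more events may be graded related.
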